## **12. Blinding**

Blinding is not applicable in this single group study.

## **13. Sample size determination**

The sample size is estimated by the number and availability of the staff in the participating units. It is estimated that a total of 12-20 staff will be recruited.

## **14. Data analyses**

The proportion of all the responses in the staff survey will be calculated. The numbers of abnormal vital signs, hospital admission and further medical assistance due to the adoption of the system will be counted.

The qualitative interview content will be transcribed verbatim in Chinese for further analysis. The qualitative interview transcripts will be analyzed using framework analysis to construct a coherent and logical structure from the classification of many opinions and perceptions of the system. The results will then be discussed and consolidated in the panel meetings with the co-authors.

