### 5. Outcomes

The primary outcomes include the efficiency of the system perceived by the care staff and staff perceptions on the whether the adoption of the system facilitates early detection of abnormal vital signs, facilitates early delivery of medical support, and reduces staff stress.

Ancillary outcomes include number of hospital admissions and any medical assistance due to the adoption of the system, and perceived benefits and acceptability of the care staff towards the system. The barriers and difficulties in the set-up of the system, and the concerns in choosing wireless or cable connection for the system are also explored.

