## **8. Research Questions**

The study has 3 primary research questions and 6 secondary research questions targeting care staff in the setting of residential homes for the elderly and community isolation facilities. The 3 primary research questions are:

- (1) Will care staff perceive the remote real-time health monitoring system as efficient?
- (2) Will the system facilitate any early detection of abnormal vital signs?
- (3) Will the system facilitate early delivery of medical support?

The 6 secondary research questions are:

- (4) What are the numbers of hospital admissions and further medical assistance due to the adoption of the system?
- (5) Will the system reduce the stress level of the care staff?
- (6) What are the perceived benefits and acceptability of the care staff towards the system?
- (7) What should be considered when developing the evaluation framework for the adaption of the system in elderly residential setting?
- (8) Are there any barriers and difficulties in the set-up of the system?
- (9) What are the concerns in choosing wireless or cable connection for the monitoring device?

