## **9. Study design**

This is a single-group 4-week trial of using the remote health monitoring system. All care staff who manage the system will complete a very brief survey (1-minute) after each work shift for 2 weeks. Detection of abnormal vital signs will be recorded by the system. Hospital admission and further medical assistance due to the adoption of the system will be counted by the care team. The care staff will be interviewed about the set-up of the system, their perceived benefits and acceptability of the system.

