### **11.2 Data collection**

The remote monitoring system will remotely and real-time record the temperature, pulse and SpO2 of the residents wearing the sensor. When the staff are notified of any abnormal vital signs by the system via screen display and notification sound, they will deliver further medical assistance. Hospital admission and further medical assistance due to the adoption of the system will be counted by the care team under pre-existing practice. After every shift during the trial period for 2 weeks, the staff will fill in a 1-minute survey about their operation and perceived efficiency of the system, such as facilitating more frequent monitoring of particular residents' vital signs, the provision of further medical assistance, perceived time saving in monitoring vital signs, and acceptability of the system. They could record their experience of using the system in written format or in a mobile phone messaging app (such as Whatsapp) in audio format. If they fill in the survey for fewer than 8 times during the 2 weeks, they would be invited to continue to fill in the survey after work shift for an extra week until they fill in it for at least 8 times. Meanwhile, as a staff

may complete more than 1 shift per day, they would not be invited to fill in the survey after having completed it for 12 times. At the end of the trial, HOHCS staff will provide the number of abnormal vital signs recorded by the system, number of hospital admissions and further medical assistance without any personal identifiers to HKU research team. All data collected that is related to residents is not identifiable.

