There are two parts of the qualitative sub-study. When the system is set up, the unit IC and care staff responsible to set up the system from each participating unit will be interviewed by HKU research assistant(s). Themes of qualitative questions include: (1) barriers and difficulties in the set-up of the system; and (2) the concerns in choosing wireless or cable connection for the monitoring device. Meanwhile, when the main trial ends, a total of 9-15 care staff from all participating units responsible to operate the system will be interviewed about their perceived benefits and acceptability of the system. Themes of qualitative questions include: (1) Acceptance of using the remote health monitoring system (including ease of operation, care staff's confidence and convenience in using the system); (2) Benefits of using the remote health monitoring system (including usefulness of the innovation, impacts on quality of care); (3) Concerns in using the remote health monitoring system (including if any residents stop using the sensor and the reason behind); and (4) Overall perception of using the remote health monitoring system. For both parts of the qualitative sub-study, an interview guide with open-ended and iterative questions will be used to probe for more experiences from the interviewees. Each interview will be conducted by a trained research assistant and will last about 15 - 30 minutes.

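### Section 14 summarises the repeated staff survey only as a proportion of responses; a per-person summary and staff denominators would show whether support is broad or split (minor, cheap improvement)

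*Combined protocol and SAP*

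**What the plan says.** Section 5 states that "The primary outcomes include the efficiency of the system perceived by the care staff", and the first primary question in Section 8 asks "Will care staff perceive the remote real-time health monitoring system as efficient". Section 9 says that all staff who manage the system "will complete a very brief survey (1-minute) after each work shift for 2 weeks".

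Section 11.2 regulates the number of answers per person. Staff with fewer than 8 completions in the two weeks are told that "they would be invited to continue to fill in the survey after work shift for an extra week", with the aim of reaching 8. At the other end, "they would not be invited to fill in the survey after having completed it for 12 times". The survey topics include more frequent monitoring of particular residents and "the provision of further medical assistance, perceived time saving in monitoring vital signs, and acceptability of the system". Section 13 expects 12-20 staff, based on availability.

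Section 14 then gives one survey summary: "The proportion of all the responses in the staff survey will be calculated". The rest of that section covers event counts and a framework analysis of interviews. On the interviews, Section 11.2 says that at the end of the trial "a total of 9-15 care staff from all participating units responsible to operate the system will be interviewed"; these are analysed qualitatively. No section says how one person's several answers are to be combined.

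**The concern.** The outcome and the question are about people, while the planned summary is about answers. A percentage of answers can be the same when nearly everyone is mildly in favour and when some staff are always in favour and others rarely are. Those two results would be read differently in the study's deliverable, a local testing protocol for future use of such systems in elderly residential settings. A base of 100 or 200 answers also looks like 100 or 200 respondents unless the number of staff stands beside it.

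**Working it through.** **Inputs.** Staff: n = 12 to 20 (Section 13). Surveys per person: m = 8 to 12 (Section 11.2; 8 is a target, not a guaranteed minimum). The documents give no favourable percentage, ICC or opinion gap, so the values below are assumptions. The plan has no figure of its own to reproduce, because 12-20 is an availability estimate.

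**1. Base of the pooled proportion.** If all staff fall within 8-12 surveys, the number of answers runs from 12 × 8 = 96 to 20 × 12 = 240.

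**2. What a pooled percentage leaves open (arithmetic limits).** Call a person favourable if at least m/2 of their own answers are favourable. With T favourable answers in total, k favourable staff are possible when k·m/2 ≤ T ≤ k·m + (n − k)(m/2 − 1).

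| n × m | T (pooled) | Possible k |
|---|---|---|
| 12 × 8 | 67 of 96 (70%) | 7-12 of 12 |
| 20 × 12 | 168 of 240 (70%) | 10-20 of 20 |
| 12 × 8 | 86 of 96 (90%) | 10-12 of 12 |
| 20 × 12 | 216 of 240 (90%) | 17-20 of 20 |

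An example for the first row: five staff favourable on 5 of 8 and seven on 6 of 8 give 25 + 42 = 67, with 12 of 12 favourable. Seven staff favourable on all 8, one on 3 and four on 2 give 56 + 3 + 8 = 67, with 7 of 12 favourable. These limits are extremes, not expectations.

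**3. What is more likely.** Beta-binomial model, m uniform on 8-12, expected share of staff favourable on at least half of their own surveys:

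| Assumed ICC | 0.1 | 0.3 | 0.5 | 0.7 |
|---|---|---|---|---|
| 70% of answers favourable | 86% | 78% | 74% | 72% |
| 90% of answers favourable | 99% | 95% | 93% | 91% |

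At ICC 0.3-0.7 the difference from the pooled figure is about 1-8 points. At ICC 0.1 it is larger (16 points at 70%, 9 at 90%), but part of that comes from the counting rule: at 70% and ICC 0.1, requiring more than half instead of at least half gives 80%, not 86%.

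**4. Unequal weighting.** If a fraction f of staff give 12 surveys and the rest give m₂, and the two groups' favourable proportions differ by a given gap, the pooled figure departs from the equal-weight mean by

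gap × f(1 − f)(12 − m₂) / [12f + m₂(1 − f)].

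For m₂ = 8 the maximum is at f = 0.45: 0.2475 × 4 / 9.8 = 0.101 × gap. That is about 1 point for a 10-point gap and 3 points for a 30-point gap, and zero if opinion is unrelated to the number of surveys. If some staff miss the target, say 1-3 of 12 stop at 4 and the rest give 12, the shift is 0.5-1.5 points for a 10-point gap and 1.6-4.5 points for a 30-point gap.

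**The case against.** The strongest reply is that no section promises a count of staff. The survey follows each shift, and several items describe what happened in use, so the shift is a natural unit. The study is descriptive and small, and the sentence in Section 14 may simply mean tabulating every answer option, which does not rule out a per-person table. The 8-survey target, the extra week and the cap of 12 already limit unequal weighting. Most of this stands. A share of shifts is a fair description and should be kept. But on the tabulation reading, too, the unit is unstated and no staff-level result is specified, and perception and acceptability are properties of people.

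A reader might infer three stronger things, none of which the documents support:

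- **That pooling makes the inference invalid.** No test or interval is planned, so there is no stated precision or error rate to be wrong.
- **That the result could be wildly off.** The wide ranges in step 2 need contrived response patterns.
- **That a count of staff in favour is a required endpoint.** It is not. Any such count also depends on an arbitrary cut-off, which in the example above moves the share by 6 points, more than the weighting effect within 8-12 surveys.

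Per-person results carry a cost as well. Results go to the participating service (Section 20), Section 21 protects staff from consequences for their work appraisals, and with 12-20 people individuals could be recognised.

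**Conclusion.** Minor: a cheap improvement, not an error in the plan. Section 14 gives a valid description of shifts but leaves unshown whether favourable opinion is spread across staff or concentrated in some of them, and it does not require the number of people behind the percentage to be stated. The likely effect on the reading is about 1-8 points for the staff share at ICC 0.3-0.7, and about 0-3 points for weighting within 8-12 surveys. The ICCs, the 70% and 90% levels, the opinion gaps and the two-way favourable coding are all assumptions. The survey form is not in the supplied text (Section 16 lists it as still to be prepared), so its items and response scale could not be checked.

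**What to change.** Keep the response-level proportion and add to Section 14:

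> *For perception and acceptability items we also report the distribution (median and range) and the equal-weight mean of per-person proportions, with the number of staff and the number of surveys per person shown beside every pooled proportion. Favourable categories are fixed before the data are examined.*

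A count of staff favourable on most of their own surveys is optional. If it is given, fix the cut-off and the handling of ties in advance. No interval is needed; if one is ever shown, it should not treat the responses as independent.

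**Cost.** A few sentences and a little more analysis, with no extra data collection from staff. Each survey must carry a staff code. The limits of 8 and 12 already require counting completions per person, but linking the answers to a code is a further step. To limit identifiability, use pseudonymous codes held by the research team, and suppress by-unit or per-person displays where cells are small.

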## **15. Risk Control & Contingency Planning**

Outbreak of infectious disease in the society/service unit that might limit the access of the research staff to carry out qualitative study. As a contingency plan, the qualitative interview can be done via virtual platform (e.g. WhatsApp or Zoom).

For damage and repair of any components during the testing period, the product supplier will provide sufficient number of devices as back-up with a 3-month warranty for the new device and maintenance.

As a voluntary participation, the participants have the right to withdraw from the study and intervention any time without consequences.

In case of inclination of product developers to produce positive test results, the research investigators will maintain research independence by excluding the product developer in data analysis and evaluation report writing.

## **16. Time-line: (HOLD\*3 study)**

HKU to prepare research instruments (staff survey etc.)	March 2022
Perform trial and monitoring for the main trial	March 2022 –
Carry out qualitative study	April 2022
Perform data cleaning and analysis	
Prepare datasets for data entry	April 2022 –
Data entry	June 2022
Transcription	
Summarization of transcripts by Nvivo	
Data analysis and tabulation	

**17. Describe any unusual or discomforting procedures to be used:** Nil.

**18. Are there any hazards associated with the investigation?** No.

**19. Direct access to source data/documents**

The raw data will be stored in the CD-ROM and locked in a cupboard with keys kept by the Principal Investigator. Only the Investigators and Research Assistant of the project will be permitted to access to raw data and/or study record. The data will be kept for 10 years or longer after the study completed.

## **20. Dissemination of study result**

Study results will be made available for the funder, Gerontechnology Platform (GTP), and Haven of Hope Christian Service (HOHCS). Upon the agreement of the funder and product supplier, study results shall be made available presented in international conferences such as International Conference on Gerontechnology and published in internationally ranked journals, such as Gerontechnology Journal and International Journal of Nursing Studies.

## **21. Consent**

Care staff responsible for the operation or installation of the remote health monitoring system will be invited to participate in the study by obtaining written consent. The HKU researcher or the investigator not responsible for the home will explain to the relevant details of the study before seeking consent. As a voluntary participation, the participants have the right to withdraw from the study any time without consequences to their rights or their work appraisals.

## **22. Conflict of interest: None**

## **23. Financing and insurance**

This research will be funded by the Social Innovation and Entrepreneurship Development Fund.

